9.7. Physical Evaluations

Physical examinations including skin, head and neck including upper respiratory tract (nares and nasopharynx), lungs including wheezing, heart, liver, spleen, extremities, lymph nodes, and nervous system will be performed at screening visit. Limited physical examinations to specifically include the nares (including edema), throat, and lungs (including evaluation for wheezing as well as other body systems if indicated based on review of medical history) will be performed at the enrollment visit (Day 1) and approximately Day 8. The grading scale for erythema (redness) and induration (swelling or edema) detected in these exams are provided in [Table 8](#). Targeted physical examinations may be performed at any other clinic visit if indicated based on review of medical history. Any changes in physical examination data from screening will be summarized for each visit by study arm for subjects in the Safety population ([Listing 16](#)).

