## 4. STUDY DESIGN

This is a Phase I double-blind, randomized, placebo-controlled study in 50 healthy adolescents and children, 9-17 years of age, who are in good health and meet all eligibility criteria. The study is designed to assess the safety and immunogenicity of a prime-boost regimen of H3N2 M2SR intranasal influenza vaccine followed by licensed inactivated QIV boost administered IM. Group A will receive one dose of M2SR intranasally on Day 1 and one dose of QIV on Day 92. Group B will receive one dose of saline intranasally on Day 1, and one dose of QIV on Day 92. See Table 1 for the randomization scheme for this trial.

The two treatment arms will be enrolled and vaccinated concurrently.

Reactogenicity will be measured by the occurrence of solicited upper respiratory, respiratory tract assessment, and systemic reactions from the time of the experimental (first) study vaccination through 7 days after vaccination. Unsolicited non-serious AEs will be collected from the time of the first study vaccination through approximately 21 days after the first study vaccination. SAEs will be collected from the time of the first study vaccination throughout the entire study. AESIs (wheezing, and otitis media) and NOCMC will be documented and reported from the time of first study vaccination through approximately 3 months after first study vaccination.

Immunogenicity testing will include performing HAI, HA/NA ELISA, neutralization, nasal secretory IgA (sIgA), IFN- $\gamma$  ELISPOT and CFSE dilution/ICS assays. Serum for HAI, HA/NA ELISA and neutralization assays will be obtained on Day 01 (pre-vaccination), Days 08, 22, and 57 after the first vaccination, immediately prior to the 2nd study vaccination (Day 92), and on Day 22 after the 2nd vaccination. Nasal swabs for sIgA will be collected on Day 01 (pre-vaccination), Days 08, 22, and 57 after the first vaccination, immediately prior to the 2nd vaccination (Day 92), and on Day 22 after the 2nd vaccination. PBMC for T cell functional assays (IFN- $\gamma$  ELISPOT and CFSE dilution/ICS assays) will be harvested on Day 01 (pre-vaccination), Days 08, 22, and 57 after the first vaccination, immediately prior to 2nd vaccination (Day 92), and on Day 22 after the 2nd vaccination.

The duration of this study for each subject will be approximately 13 months.

---

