- Approximately 16 mL of PBMCs will be collected for IFN- $\gamma$  ELISPOT and CFSE dilution/ICS assays.
- A urine pregnancy test will be performed on all female adolescent subjects of childbearing potential and must be negative to ensure eligibility.
- Subjects will be enrolled in AdvantageEDCSM and assigned randomly to a treatment arm prior to the first study vaccination.
- Pre-administration reactogenicity assessments will be performed prior to the first study vaccination to establish baseline. Subjects will then receive a single dose of study product or placebo intranasally. Subjects will be observed in the clinic for at least 30 minutes after the first study vaccination. Post-administration reactogenicity assessments will be completed, and any AE/SAEs will be recorded on the appropriate data collection form prior to discharge from the clinic.
- Parent(s)/legal guardian(s) will be provided with a memory aid and other study-related materials to record daily oral temperature, solicited systemic reactions, any unsolicited AEs, and concomitant medications. Parent(s)/legal guardian(s) will be encouraged to take child's oral temperature around the same time each day. Subjects must not eat or drink anything hot or cold, or smoke within 10 minutes prior to taking oral temperature. Parent(s)/legal guardian(s) will be instructed on how to use their memory aid and how to measure and record AEs prior to discharge from the clinic. Parent(s)/legal guardian(s) will be instructed to notify the study center if they develop any severe reactions after the first study vaccination. If the site principal investigator or appropriate sub-investigator deems the reaction severe enough, further instructions will be given to the parent(s)/legal/guardian(s) on the proper course of action, including a return to the clinic for immediate evaluation if appropriate.

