- At the screening visit a physical examination will be performed on all subjects to include the following organs and organ systems: including skin, head and neck including upper respiratory tract (nares and nasopharynx), lungs, heart, liver, spleen, extremities, lymph nodes, and nervous system, by a study clinician licensed to make medical diagnoses and listed on the Form FDA 1572 as the site principal investigator or sub-investigator. At Visit 01, 02 and Early Termination or Unscheduled Visits if they occur within 8 days of vaccination after the first study vaccination, a limited physical examination to include the nares (including edema), throat, and lungs will be performed and a targeted physical examination may be performed on the other body systems, if indicated based on the subject's interim medical history, by a study clinician licensed to make medical diagnoses and listed on the Form FDA 1572 as the site principal investigator or sub-investigator. At all other follow-up visits, a targeted physical examination may be performed, if indicated based on review of interim medical history, by a study clinician licensed to make medical diagnoses and listed on the Form FDA 1572 as the site principal investigator or sub-investigator.

Oral temperature will be collected prior to each study vaccination. Subjects must not eat or drink anything hot or cold, or smoke within 10 minutes prior to taking oral temperature.

Reactogenicity assessments will include an assessment of solicited AEs occurring from the time of experimental (first) study vaccination through Day 8 after vaccination. For upper respiratory symptoms, this includes an assessment of runny nose, stuffy nose/ congestion, sneezing, nasal pain/irritation/nasal dryness, nasal bleeding/epistaxis, sinus pressure/pain, sore throat/sore/scratchy, itchy or painful throat, cough, trouble breathing/shortness of breath. For general systemic symptoms, this includes an assessment of reactions including fever, feverishness (chills/shivering/sweating), fatigue (tiredness), malaise, myalgia (body aches/muscular pain), arthralgia (joint pain), headache, flushing, decreased activity, decreased appetite, abdominal pain, nausea, vomiting, diarrhea, eye pruritus, eye redness (conjunctivitis), and allergy. For respiratory tract symptoms, this will include an assessment of nares' erythema and induration.

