## 9. ASSESSMENT OF SAFETY

### 9.1 Specification of Safety Parameters

Safety will be assessed by the frequency and severity of:

1. SAEs occurring from the time of the first study vaccination through 12 months after the first vaccination.
2. AESIs (wheezing, otitis media) and NOCMCs occurring from the time of the first study vaccination through 3 months after the first vaccination.
3. Solicited Adverse Events – reactogenicity events occurring from the time of experimental (first) study vaccination through 7 days after the first study vaccination. See tables listed in [section 9.2.2 and 9.2.6](#) for local upper respiratory, respiratory tract assessment, and systemic symptoms:
4. Unsolicited Non-Serious Adverse Events –non-serious AEs occurring from the time of the first study vaccination through approximately 21 days after the first study vaccination.
5. Clinical safety laboratory AEs occurring at approximately 7 days after the first vaccination. Parameters to be evaluated include a WBC, HGB, Platelet Count, ALT, AST, Serum Creatinine, Ferritin level, PT and aPTT. HGB will also be repeated at Day 22 if there is a drop in HGB level from screen to Day 8 of  $\geq 0.5$  g/dL or results are  $<$  lower limits of normal. If unable to collect at Day 22, collect at Day 57. If drawn at Day 22 and the results are still low, repeat at Day 57. If HGB results are still low at Day 57, no further PBMC collection will be done. HGB and Ferritin level will be drawn at Day 113. If the ferritin is  $< 15$  ng/mL and/or the HGB is less than the lower limits of normal, will recommend follow-up with primary care provider for consideration of multivitamins with iron.

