### 9.2.6. Respiratory Tract Assessment Grading: Erythema and Induration

Erythema and Induration of the nasal cavity will be graded as follows:

Parameter	Grade 1	Grade 2	Grade 3
Erythema (Redness)	Very slight or barely perceptible redness	Well defined redness	Moderate to severe beet redness to eschar

Parameter	Grade 1	Grade 2	Grade 3
Induration (Swelling or edema)	Very slight or barely perceptible swelling	Slight swelling (edges of area well-defined by definite raising)	Moderate swelling (edges raised approximately 1 mm)

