### **9.3. Reporting Procedures**

Solicited upper respiratory assessment, respiratory tract assessment, and systemic reactogenicity events will be documented and reported from the time of experimental (first) study vaccination through 7 days after vaccination.

Unsolicited non-serious AEs will be documented and reported from the time of the first study vaccination through approximately 21 days after the first study vaccination.

SAEs will be documented and reported from the time of the first study vaccination through 12 months after the first vaccination.

AESIs (wheezing and otitis media) and NOCMCs will be documented and reported from the time of first study vaccination through approximately 3 months after first study vaccination.

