#### **11.4.2. Primary Safety Data**

Summaries and analysis of safety data will be presented for the Safety Analysis Population.

Solicited AEs will be summarized by severity for each day after the first study vaccination (Days 1-8 post vaccination) and as the maximum severity over all 8 days. Additionally, solicited AEs will be analyzed by taking the most severe response over the follow-up period, dichotomizing into a binary variable (none versus mild, moderate, or severe) and using standard techniques, such as exact confidence intervals, to summarize the number and percentage of subjects reporting each symptom, any upper respiratory symptom and any systemic symptom by treatment arm.

Unsolicited AEs will be coded by Medical Dictionary for Regulatory Activities (MedDRA®) for preferred term and system organ class (SOC). The number of SAEs, AESIs, and NOCMCs is expected to be small in this trial and will be reported by detailed listing showing the event description, MedDRA preferred term and SOC, relevant dates (study vaccinations and AEs), severity, relatedness, and outcome for each event. If more than 5% of subjects report SAEs, and AESIs, and NOCMCs then the number and percentage of subjects reporting each type of event will be reported by treatment arm and compared using Fisher's Exact test. Unsolicited AEs will be summarized as number and percentage of subjects reporting at least one event in each MedDRA preferred term and SOC, cross tabulated by severity and relationship to study product. Additionally, the proportion of subjects and exact 95% confidence intervals of AEs in aggregate and by MedDRA categories will be computed.

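### No SAP table reports nasal redness and swelling by grade and arm, although the protocol grades both as solicited reactions to the intranasal vaccine.

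*SAP*

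**What the plan says.** Four protocol sections put the respiratory tract assessment among the solicited reactions.

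- Section 4: "Reactogenicity will be measured by the occurrence of solicited upper respiratory, respiratory tract assessment, and systemic reactions".
- Section 8.1, describing the solicited assessments: "For respiratory tract symptoms, this will include an assessment of nares' erythema and induration".
- Section 9.1, under solicited adverse events, refers to the grading tables in 9.2.2 and 9.2.6 "for local upper respiratory, respiratory tract assessment, and systemic symptoms".
- Section 9.3: "Solicited upper respiratory assessment, respiratory tract assessment, and systemic reactogenicity events will be documented and reported".

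Section 9.2.6 supplies the scale: "Erythema and Induration of the nasal cavity will be graded as follows", with Grades 1 to 3 for each sign. Section 11.4.2 sets the analysis: "Solicited AEs will be summarized by severity for each day after the first study vaccination", then by maximum severity, and as number and percentage per symptom by arm. Section 7.3.1 sets the reference point: "Pre-administration reactogenicity assessments will be performed prior to the first study vaccination to establish baseline".

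The SAP keeps the assessment within reactogenicity (4.1, at Visit 02) and reproduces the scale (Table 8). Its section 9.7 says that "Any changes in physical examination data from screening will be summarized for each visit by study arm for subjects in the Safety population" and cites Listing 16.

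**The concern.** Safety is the trial's only primary objective, and the vaccine is sprayed into each nostril. Redness and swelling of the nares are the graded examination findings at that site. The SAP carries their grading scale but specifies no results table that uses it. A reader of the study report who wanted the number of affected children per arm would have to rebuild it from a listing that does not show the grade.

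**Working it through.** This is mainly a comparison of texts. The arithmetic is a row count and an illustration of what the missing rows would show.

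**1. Solicited-event list.** SAP 9.3.1 names nine local events: runny nose, congestion, sneezing, nasal pain or irritation, nasal bleeding, sinus pressure or pain, sore throat, cough and trouble breathing. Neither nasal erythema nor nasal induration is among them or among the systemic events.

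**2. Table shells.** Leaving aside the Any rows, Table 40 has 17 systemic symptom rows (feverishness through wheezing) and 9 local rows: 17 + 9 = 26. Rows for nasal erythema or induration: 0 of 26. Tables 41 to 43 repeat the same symptoms, and Table 44 takes the format of Table 43. Of the 68 table titles in the SAP, only Table 8 names the two signs, and it is a grading scale.

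**3. The display cited in 9.7.** The columns of Listing 16 are study group, subject ID, planned time point, actual study day, body system, abnormal finding and whether it was reported as an AE. There is no grade and there are no counts, and subjects without findings are left out. It cannot deliver a summary by visit and arm, and severity cannot be recovered from it.

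**4. Comparison with wheezing.** Wheezing is also graded at Visit 02 (protocol 9.2.4). SAP 9.3.1 declares it solicited, and it has rows in Tables 40 to 43, with the Day 1 to Day 7 cells in Table 43 marked NA. The shells can therefore take a sign that is not recorded daily.

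**5. Baseline.** SAP 9.7 measures change from screening, which may be up to 28 days before dosing. Protocol 7.3.1 sets the pre-dose reactogenicity assessment on Day 1 as baseline, and the Day 1 limited examination covers the nares.

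**6. What the missing rows would show.** The documents give no expected rate, so these counts are illustrative. The inputs are the planned n = 25 per arm and the Blaker method named in SAP 9.3.1. The 95% interval is the set of p for which the smaller tail probability at the observed count, plus the largest opposite-tail probability not exceeding it, is at least 0.05.

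| Count | Percentage | Blaker 95% CI | Clopper-Pearson 95% CI (check) |
|---|---|---|---|
| 0/25 | 0% | 0% to 12.8% | 0% to 13.7% |
| 2/25 | 8% | 1.4% to 25.2% | 1.0% to 26.0% |
| 5/25 | 20% | 8.2% to 39.7% | 6.8% to 40.7% |

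For 0/25 the Clopper-Pearson upper limit is 1 − 0.025^(1/25) = 13.7%.

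**The case against.** The strongest reply is that SAP 9.7 already promises a summary by arm, so only a shell and a cross-reference are missing. That describes the defect correctly but does not remove it: the sentence names a display that cannot deliver the summary, and no other display is specified.

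Second, the shells are incomplete in another place. SAP 9.3.1 lists fever, yet Tables 40 to 43 have a row for feverishness and none for fever, so an absent row need not mean exclusion. This weakens the row count as evidence. Fever, however, is at least named in the 9.3.1 text, and the two nasal signs are not.

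Third, some protocol wording is narrower. The primary outcome (3.2.1), section 9.2.2 and the composites in 11.4.2 name only upper respiratory and systemic reactions. The day-by-day summary in 11.4.2 also fits the memory aid better than a single clinic examination. This stands as a reason to keep the signs out of the composites. It does not override sections 4, 8.1, 9.1 and 9.3, and the per-symptom summary by arm needs no daily data.

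Fourth, a finding entered as an unsolicited AE would reach Table 46 by severity and arm, and Listing 12 admits clinic examination data with severity. The first route depends on investigator entry and may miss mild signs. The second is a listing of local symptoms, which 9.3.1 defines without these two. Neither is specified for them.

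Fifth, screening is a defensible reference for physical examinations in general, since protocol 9.2.1 treats conditions present at screening as baseline for AEs. For a solicited reaction, 7.3.1 is the more specific rule.

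Finally, other nasal symptoms are tabulated by grade, day and arm, so nasal tolerability is not wholly unreported. That limits the loss to the two examination signs.

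**Conclusion.** The concern holds. The protocol defines and grades nasal erythema and induration as solicited reactions, and the SAP specifies no table of either by grade and arm (0 of 26 symptom rows in Table 40; no results table among 68 titles). The consequence is confined to final safety reporting. Halting rules and SMC review run on AE reporting and are not affected. No effect on Any Local Symptom is claimed, because neither document places these signs in that composite. The conclusion rests on reading protocol sections 4, 8.1, 9.1 and 9.3 as controlling over the narrower wording of the primary outcome, and on the SAP being followed as written. The intervals above show what would be reported; they do not measure a bias.

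**What to change.** Add nasal erythema and nasal induration rows to SAP Tables 40 to 42, or one separate table cited in 9.7. Report by arm at Day 8 in the Safety population: number and percentage at Grades 0, 1, 2 and 3 as recorded, with the Blaker intervals already planned for solicited events. Use the Day 1 pre-dose assessment as baseline instead of screening. Keep the rows separate from Any Local Symptom unless the SAP defines them as part of it. Add a grade column to Listing 16 and correct the reference in 9.7.

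The cost is two rows in three shells, or one small table, plus one listing column. No new visit or examination is needed, because the Day 8 assessment is already planned and graded. The Day 1 grade is assumed to be recorded, because SAP 9.7 names the Day 1 and Day 8 examinations and then applies the Table 8 scale to them. If it is not recorded, the Day 8 grades can be shown alone.

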9.8. Concomitant Medications

Concomitant medications will be collected in the database for the 30 days prior to the first study vaccination through 21 days after the second study vaccination. Concomitant medications will be coded to the Anatomical Therapeutic Classification using the WHO Drug Dictionary. The use of prior and concomitant medications taken during the study will be recorded on the CRFs. A by-subject listing of concomitant medication use will be presented ([Listing 17](#)). The use of concomitant medications during the study will be summarized by ATC1, ATC2 code and treatment group for the Safety population ([Table 68](#)).

10. REPORTING CONVENTIONS

P-values ≥ 0.001 and ≤ 0.999 will be reported to 3 decimal places; p-values less than 0.001 will be reported as “<0.001”. The mean, standard deviation, and other statistics will be reported to 1 decimal place greater than the original data. The minimum and maximum will use the same number of decimal places as the original data. Proportions will be presented as 2 decimal places; values greater than zero but <0.01 will be presented as “<0.01”. Percentages will be reported to the nearest whole number; values greater than zero but < 1% will be presented as “<1”; values greater than 99% but less than 100% will be reported as >99%. Estimated parameters, not on the same scale as raw observations (e.g. regression coefficients) will be reported to 3 significant figures.

11. TECHNICAL DETAILS

SAS version 9.4 or above will be used to generate all tables, figures and listings.

12. SUMMARY OF CHANGES IN THE CONDUCT OF THE STUDY OR PLANNED ANALYSES

Enrollment into Protocol 17-0012 was paused in November 2018 for safety concerns and revision as follow:

- Subjects enrolled beyond early November would receive the protocol-provided QIV at an unacceptably late time in the 2018-2019 influenza season.
- Consistent drops in HGB post first vaccination had been noted among the subjects enrolled in 2018.

As a result, the protocol was updated to include additional blood draws past Visit 02 to confirm that low HGB values return to normal, or to implement a clinical plan for subjects who do not return to normal (see Section 9.6 for further details). Enrollment is to resume in 2019 to enroll the remaining 31 subjects, which will allow sufficient time to receive the QIV vaccination prior to the 2019-2020 influenza season. An interim analysis of the subjects enrolled in 2019 was added to the protocol at this time.

The plan to pursue exploratory anti-NA antibody assays was changed from being depending on observing increased sIgA response to the M2SR H3N2 strain in the M2SR vaccinated group, to being contingent on observing increased HAI or MN seroconversion or 4-fold rise rates in the M2SR vaccinated group compared to placebo post M2SR vaccination (see Section 8.3).

14. LISTING OF TABLES, FIGURES, AND LISTINGS

Table, figure, and listing shells are presented in Appendices 1, 2, and 3.

APPENDICES

9.1 Overall Study Design and Plan Description**Table 1: Study Design**

Treatment Arm	Subjects	First Study Vaccination	Second Study Vaccination
Group A	25	M2SR	QIV
Group B	25	Placebo	QIV

9.5.1 Efficacy/Immunogenicity and Safety Measurements Assessed and Flow Chart**Table 2: Schedule of Study Procedures**

Study Visit Number	V00	V01	V02	V03	V04	V05	V06	V07	V08	Early Term	Unscheduled
Study Day post first study vaccination	Screen -28 to -1	Dose 1* D1	D8 ±1	D22 ±2	D57 ±3	Dose 2* D92 ±14	D113	D240	D366		
Study Day post second study vaccination						D1	D22 ±2	D149±14	D275±14		
Obtain Informed Consent/Assent	X										
Collect Demographic Information	X										
Review Eligibility Criteria	X	X				X					
Medical History	X	X	X ¹	X ¹	X ¹	X	X	X	X	X	X
Concomitant Medications	X	X	X	X	X ²	X ²	X ²			X ^{#3}	X ^{#3}
Counsel about avoidance of taking aspirin and salicylate containing products	X	X	X	X	X	X	X			X	X
Oral Temperature		X				X				X	X
Physical Examination	X										
Limited Physical Examination		X	X							X [@]	X [@]
Age and developmentally appropriate counseling about pregnancy prevention	X	X									
Targeted Physical Exam			{X}	{X}	{X}	{X}	{X}			X	X

Table 2: Schedule of Study Procedures (Continued)

Study Visit Number	V00	V01	V02	V03	V04	V05	V06	V07	V08	Early Term	Unscheduled
Study Day post first study vaccination	Screen -28 to -1	Dose 1* D1	D8 ±1	D22 ±2	D57 ±3	Dose 2* D92 ±14	D113	D240	D366		
Study Day post second study vaccination						D1	D22 ±2	D149±14	D275±14		
Urine Pregnancy Test	X^	X^				X^					
WBC, HGB, HCT, Platelet Count, ALT, AST, Serum Creatinine, PT, and aPTT	X		X	X ^{4,5}	X ^{4,6}		X				
Ferritin Level							X				
Serum (HAI, HA/NA ELISA, Neutralization Assays)		X	X	X	X	X	X			X	
Nasal Swab sIgA		X	X	X	X	X	X			X	
PBMC (IFN-γ ELISPOT and CFSE Dilution/ICS Assays)		X	X	X	X	X	X			X	
Whole Blood for Future Research		X	X	X							
Enrollment in AdvantageEDC SM and Randomization		X									
Pre-Administration Reactogenicity		X				X					
Study Vaccination		X				X					
30-minute Evaluation After Study Vaccination		X				X					
Distribute Memory Aid and Study-Related Materials		X									

Table 2: Schedule of Study Procedures (Continued)

Study Visit Number	V00	V01	V02	V03	V04	V05	V06	V07	V08	Early Term	Unscheduled
Study Day post first study vaccination	Screen -28 to -1	Dose 1* D1	D8 ±1	D22 ±2	D57 ±3	Dose 2* D92 ±14	D113	D240	D366		
Study Day post second study vaccination						D1	D22 ±2	D149±14	D275±14		
Review Memory Aid			X							X [@]	X [@]
AE Assessment		X	X	X						X [#]	X [#]
AESI + NOCMC Assessment			X	X	X	X				X [!]	X [!]
SAE Assessment		X	X	X	X	X	X	X	X	X	X
Phone Call								X	X		

{} Targeted physical examination if indicated based on review of complete or interim medical history
[^]Will be performed on all female adolescents of childbearing potential at screening and within 24 hours prior to each study vaccination and results must be negative and known prior to each study vaccination.
[#]If within 21 days post first study vaccination.
^{*}On dose dates, samples must be collected pre-dose
[@]If within 8 days after 1st vaccination
[!]If within 3 months post first study vaccination
¹Subject's parent(s)/legal guardian(s) will be asked if the subject had any additional blood taken for medical reasons.
²Concomitant medications will be limited to collecting aspirin and salicylate containing products
³Aspirin or salicylate containing products will be collected if within 30 days of the first vaccination through 21 days after the last vaccination
⁴Hemoglobin only
⁵Collect at Day 22 if Hgb results from screen to Day 8 drop ≥ 0.5 g/dL or < lower limits of normal
⁶If Hgb is not collected at Day 22 or low at Day 22, collect at Day 57

